8.3 STUDY DATABASE

The study database will be created and maintained by ECTU. The database will be compliant with the relevant regulations and Sponsor Standard Operating procedures (SOPs) Trained and delegated members of the research team will be given password protected logins to the database. The data will be stored on a secure server in the University of Edinburgh

8.4 ARCHIVING OF STUDY DATA

All trial related and source documents should be archived for three years after the study end date in accordance with the Sponsor's archiving policy,

CR007-T02 v0.5 Page **40** of **69**

IRAS 299977/308830

Version 5.0 26Jun2024

8.5 ARCHIVING OF CENTRAL DATA

All trial related documents will be archived for three years in accordance with the Sponsor's archiving policy unless an alternative longer archiving period is specified by the sponsor or the funder.

8.6 DATA CONTROLLER

The University of Edinburgh and NHS Lothian are joint data controllers along with any other. entities involved in delivering the study that may be a data controller in accordance with applicable laws

8.7 DATA BREACHES

Any data breaches will be reported to the University of Edinburgh and NHS Lothian Data Protection Officers who will onward report to the relevant authority according to the appropriate timelines if required.

9 STATISTICS AND DATA ANALYSIS

9.1 SAMPLE SIZE CALCULATION

Sample size calculations were informed by our pilot studies, the 2019 NHFD Annual Report, the FOCUS trial (US-based pre-2010), other observational studies and expert opinion. In people with hip fracture, we estimate 30-day all-cause mortality will be 7%, rates of MACE will be 10% and rates of new MINS will be 20%. Note these rates reflect 'whole population' outcome rates and are expected to underestimate rates seen in the proposed trial population (enriched by anaemia status which is associated with higher death and MACE event rates).

Rates of cardiac injury and death in anaemic participants are likely to be higher (as in our pilot trial), and components will occur concurrently in some participants. Conversely, routine Troponin/ECG measurement may increase MI detection compared to previous studies. Overall, we estimate a population 'usual care' MACE rate (including death) of 10% at 30 days. We estimate the rate of new MINS in this population to be 20% based on pilot data. Based on clinical consensus among UK opinion-leaders/experts, we consider an absolute risk reduction (ARR) of 5% in the primary outcome to be a realistic meaningful effect size that would change practice (33% Relative RR). Importantly, this would represent a number needed to treat (NNT) of 20 for every patient receiving liberal transfusion to avoid a death and/or MACE outcome compared to the restrictive group.

We recognise limitations of a composite primary outcome treated as a binary (yes/no) indicator, because components treated equally may have differing importance to patients and clinicians. Importantly, nonfatal and/or less severe parts of the composite may occur more frequently and might dominate overall event rates. We will address this with an ordinal ranking of the possible outcomes at 30 days (1 best; 6 worst) according to severity/importance:

CR007-T02 v0.5 Page **41** of **69**

IRAS 299977/308830

Version 5.0 26Jun2024

[1] No death, no MACE, no new MINS
[2] No death, no MACE, but new MINS.
[3] No Death ≥1 MACE
[4] Death, no MACE, no new MINS;
[5] Death, plus new MINS
[6] Death plus ≥1 MACE.

We will also report rates of MACE components and new MINS separately.

Thus the assumed 30 day mortality rate is 7%, MACE at 30 days is 10%, and rate of new MINS is 20%. To detect a 30% RRR (corresponding to a log-odds-ratio of approximately 0.64) and assuming proportional odds (34) between the liberal and restrictive groups, we require a sample size of 507 participants in each arm, using a Wilcoxon-Mann-Whitney rank-sum test with a 5% two-sided significance level and 90% power. Allowing for a 10% dropout rate, we propose to recruit 563 participants per group. Total sample size 1126 participants.

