The secondary outcomes at 30 days will be: all-cause mortality, myocardial injury, individual MACE components, new MINS, other complications (acute kidney injury (AKI), infection, delirium); proportion transfused; volume of blood transfused; discharge destination; hospital length of stay; and healthcare related quality of life (HRQoL) using EQ-5D-5L.

The *secondary outcomes at 120 days* will be: all-cause mortality, secondary care costs up to 120 days; HRQoL (EQ-5D-5L), unplanned hospital readmissions within 120 days, mobility, residential status.

Health Economic evaluation: 120-day cost-consequence analysis and long run costutility modelling from an NHS and PSS perspective

Process evaluation: We will undertake a process evaluation in the study pilot phase to examine barriers to recruitment and protocol compliance.

Follow up: 120 days post randomisation.

Sample size: 563 per group, giving a total sample size 1126 participants (allowing 10% dropout rate). Based on pilot data and expert opinion we expect incidence rate for the primary outcome of death 7%, MACE 10% and new MINS 20% at 30 day with an absolute risk reduction (ARR) of 5% in the primary outcome to be a realistic meaningful effect size that would change practice (33% Relative RR; Number Needed to Treat, 20).

Project time frames: The total project duration is 69 months. In month 1-12 we will undertake approvals, set-up, and 10-site internal pilot. In months 13 - 45 we will setup the remaining 20 sites. Month 25 - 57: will be the main recruitment phase. In months 58-69 we will complete follow-up, analysis, report writing.

IRAS 299977/308830

Version 5 26Jun2024

Expertise: The proposed trial has been developed by an experienced multiprofessional team with patient and public involvement throughout.

PLAIN ENGLISH SUMMARY

IMPORTANCE OF PROBLEM

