1.2.4 Desirable study outcome

In people with hip fracture, we estimate 30-day all-cause mortality will be 7%, rates of MACE will be 10%, and rate of new MINS will be 20%. These rates may be higher in the anaemic populations being included in this study. We consider an absolute risk reduction (ARR) of 5% in the combined primary outcome of MACE, new MINS and death to be a realistic meaningful effect size that would change clinical practice (33% Relative RR). This would represent a number needed to treat (NNT) of 20 for every patient receiving liberal transfusion to avoid a death and/or MACE outcome compared to the restrictive group.

IRAS 299977/308830

Version 5.0 26Jun2024

STUDY OBJECTIVES

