1.4 ENDPOINTS

1.4.1 Primary Endpoint

The primary outcome will be death OR major adverse cardiac events (MACE) OR new myocardial injury after non cardiac surgery (new MINS) within 30 days of randomisation.

MACE will be defined as any combination of the following:

- Myocardial Infarction: Diagnosed using the 4th Universal Definitions for MI(14)
- New Arrhythmia: ECG confirmed arrhythmia resulting in a fall in mean arterial pressure of >20% and requiring pharmacological or cardioversion treatment.
- Cardiac or respiratory arrest: Resuscitation Council UK definitions
- Cardiogenic pulmonary oedema.

New MINS will be defined as : new elevated postoperative troponin above the upper reference limit (URL) with a rise/fall pattern indicative of acute myocardial injury occurring in the first 30 days (and typically within 72 h) after surgery; attributable to a presumed ischemic mechanism,

IRAS 299977/308830

Version 5.0 26Jun2024

clinical symptoms masked by sedation or analgesia in the perioperative setting, ischemic features (e.g. ECG, echocardiographic changes) not required.

To maximize validity and consistency, all participants will have troponin measured at randomisation (baseline), and then twice more in days 1 to 5, ideally on the 1st and 3rd calendar days after randomisation with all samples being at least 24h apart from each other, and 12-lead ECGs will be performed at baseline and repeated once in days 2 - 5. The primary outcome will be determined by an expert adjudication team blinded from group allocation.

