3 STUDY POPULATION

3.1 NUMBER OF PARTICIPANTS

The sample size calculated for this study is 1126 participants, with 563 in each arm of the study. This allows for a 10% dropout rate and is based on pilot data and expert opinion. We expect an incidence rate for the primary outcome of 15% at 30 days. An absolute risk reduction (ARR) of 5% in the primary outcome is a realistic and meaningful effect size that would change practice (33% Relative RR; Number Needed to Treat, 20).

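### The stated target (5-point ARR, 33% RRR, NNT 20) needs a 15% primary-outcome rate that the assumed 20% new-MINS rate rules out, and the sample size was calculated for a different effect

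*Protocol*

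**What the plan says.** Section 1.4.1 defines the endpoint as an OR-composite: "The primary outcome will be death OR major adverse cardiac events (MACE) OR new myocardial injury after non cardiac surgery (new MINS") within 30 days. Section 9.1 gives the component rates: "Thus the assumed 30 day mortality rate is 7%, MACE at 30 days is 10%, and rate of new MINS is 20" per cent. The abstract repeats them. Section 9.1 also says: "Overall, we estimate a population 'usual care' MACE rate (including death) of 10% at 30 days".

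The target effect appears in the abstract and in sections 1.2.4, 3.1 and 9.1. Section 9.1 considers "an absolute risk reduction (ARR) of 5% in the primary outcome to be a realistic meaningful effect size that would change practice" and equates it with a 33% relative reduction. The NNT of 20 is given in all four places. Section 3.1 adds the rate that this implies: "We expect an incidence rate for the primary outcome of 15% at 30 days". Section 1.2.4 describes the NNT in terms that leave out new MINS: "This would represent a number needed to treat (NNT) of 20 for every patient receiving liberal transfusion to avoid a death and/or MACE outcome". Section 9.1 has a near-identical sentence.

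The last paragraph of section 9.1 then sizes the trial on something else: a 30% relative reduction, equated with a log-odds-ratio of about 0.64, under proportional odds. It uses a Wilcoxon-Mann-Whitney test at two-sided 5% with 90% power. The result is 507 per arm, raised to 563 per arm (1126 in total) for 10% dropout. It gives neither the composite rate nor the control distribution over the six ordered categories.

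**The concern.** A composite joined by OR is at least as frequent as its most frequent component. With new MINS at 20%, a 15% primary-outcome rate is impossible. So is a 5-point reduction that is also a 33% relative reduction, because 0.05 / 0.33 is about 0.15.

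The effect offered as the reason for the sample size is therefore not the effect used to calculate it. A reader of the abstract or section 3.1 would take 1126 as the number needed for the practice-changing effect of 5 points. If the trial is in fact sized for a larger effect, a non-significant result will be read with more confidence than it deserves. Funders, ethics committees and oversight committees have also been given an inaccurate account of what the trial can detect.

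**Working it through.** **Inputs (protocol 9.1, 3.1, 1.4.1).** Death 7%, MACE 10% (10% including death in one sentence), new MINS 20%; stated composite 15%; 5-point ARR, 33% RRR, NNT 20; sizing effect 30% RRR, log-OR 0.64; two-sided 5%, 90% power; 507 evaluable per arm; 1:1 allocation.

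**1. The protocol's own figure.** The dropout step agrees: 507 / 0.9 = 563.3, and 2 × 563 = 1126. The 507 cannot be reproduced uniquely, because the control distribution is not given (see step 5).

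**2. Admissible composite rates.** Lower bound: 20%, if everyone who dies or has MACE also has new MINS. If MACE including death is 10%, the upper bound is 10 + 20 = 30%. With no overlap at all it is 7 + 10 + 20 = 37%.

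**3. The two effects on that range.** RRR of a 5-point ARR: 5/20 = 25%, 5/30 = 17%, 5/37 = 13.5%. ARR of a 30% RRR: 0.30 × 20 = 6 points (NNT 17), 0.30 × 30 = 9 points (NNT 11), 0.30 × 37 = 11.1 points (NNT 9). At no admissible rate is 5 points a 33% or a 30% reduction.

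**4. Power at 507 per arm.** Proportional-odds formula for the rank-sum test:

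n per arm = 6(1.96 + 1.2816)² / [(log OR)² × (1 − Σ p̄ᵢ³)], where p̄ᵢ is the mean of the two arms' proportions in category i. Inverted for power: Φ(|log OR| × √[n(1 − Σ p̄ᵢ³)/6] − 1.96).

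The splits over categories are my assumptions. Merging the death ranks, in order (no event / new MINS only / MACE without death / death): 80/10/3/7, 70/20/3/7 and 63/20/10/7 for composites of 20%, 30% and 37%, and 85/5/3/7 for the literal 15%.

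Worked case, 30% to 25%: OR = (0.25/0.75)/(0.30/0.70) = 0.778, log OR = −0.251, 1 − Σ p̄³ = 0.612. Then n = 63.04 / (0.0632 × 0.612), about 1630. Power at 507 = Φ(0.251 × √(507 × 0.612/6) − 1.96) = Φ(−0.15) = 0.44. Simulation of the rank-sum test (40,000 replicates) gives 0.44, and a plain two-proportion test 0.43.

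| Control composite | Power, 5-point ARR | n/arm for 90%, 5-point ARR | Power, 30% RRR | log OR (OR) of a 30% RRR |
|---|---|---|---|---|
| 15% (stated, impossible) | 68% | 893 | 58% | 0.41 (0.66) |
| 20% | 56% | 1188 | 73% | 0.43 (0.65) |
| 28.5% | 45% | 1576 | 90% | 0.47 (0.63) |
| 30% | 44% | 1630 | 92% | 0.48 (0.62) |
| 37% | 40% | 1806 | 97% | 0.52 (0.60) |

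Log-ORs are shown as magnitudes. At a fixed composite rate, other splits over the worse categories barely change these figures.

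**5. The 0.64.** On composites of 20–37% a 30% RRR is a log-OR of 0.43–0.52, not 0.64. A true log-OR of 0.64 would be a 36–42% RRR and would need only about 382 (at 20%) to 235 (at 37%) per arm. Three incompatible readings come within 3% of 507: a 30% RRR at a composite of about 28–29%; an odds ratio of 0.64 at about 31.5–34%; or a log-OR of 0.64 at about 14–15%, which is inadmissible. A mislabelled odds ratio is a plausible explanation, but the text does not settle it.

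**The case against.** The strongest defence is that the sample-size paragraph claims 90% power for a 30% relative reduction and nothing else. The protocol nowhere says it has 90% power for 5 points. On its own target the claim is attainable: 90% at a composite of about 28.5% and 92% at 30%. The component rates allow such composites, and section 9.1 expects the anaemic trial population to have higher rates than those listed. This stands. The 507 is not shown to be wrong; what is wrong is the account of what it delivers. Higher rates would not rescue the 5-point claim either, since power for 5 points falls as the composite rises.

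Four stronger readings are tempting, and the document does not support them:

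- That power for the declared triple is 44%. Taken literally the triple is 15% to 10%, with power of about 68%. The 44% belongs to 30% to 25% and rests on a composite that the protocol never states. Section 9.1 says components will overlap in some participants, so 30% is an upper value if MACE including death is 10%.
- That power is lower still for the NNT of 20 described as avoiding death or MACE. On the stated 10% rate, an NNT of 20 is 10% to 5%. With ranks 90/3/7 this has about 88% power (86% by two proportions).
- That a non-significant result could never rule out a 5-point benefit. The 95% half-width for the risk difference, taking both arms at the control rate, is 1.96 × √(2 × 0.2 × 0.8/507) = 4.9 points at 20% and 5.6 at 30%. A null or slightly adverse estimate could therefore exclude it.
- That the real target is 30% to 21%. This is only one distribution compatible with the figures.

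**Conclusion.** The point holds as an internal contradiction with consequences for stated power. That the 15% rate and the 5-point/33%/NNT 20 set cannot coexist with 20% new MINS follows from the definition of the endpoint and needs no assumption. That the justified effect differs from the sized effect is equally certain: at composites of 20–37%, 5 points is a 14–25% reduction, against the 30% used.

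The size of the shortfall depends on the unstated composite. Power for 5 points is about 40–56% across 37–20%, and about 68% for the literal 15% to 10%; no reading reaches 90%. Power for the 30% reduction ranges from 73% to 97% over the same composites and reaches 90% from about 28.5%. These figures assume proportional odds, 507 evaluable per arm and the category splits shown. The 0.64 is inconsistent with a 30% reduction at every admissible rate.

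The likely origin is wording kept from the previous endpoint. The document history records that new MINS was added and the sample cut from 1964 to 1126, and 15% to 10% gives 893 / 0.9 × 2, about 1984, close to 1964. This is an inference, and the finding does not depend on it.

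**What to change.** Keep 1126 and correct the text in the abstract and sections 1.2.4, 3.1 and 9.1:

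1. State the six-level control distribution actually used to obtain 507, and the composite rate that it implies.
2. Replace the 15% rate and the 33% relative reduction with figures consistent with that distribution.
3. State the ARR, RRR and NNT for which the trial has 90% power.
4. Correct the 0.64: say whether it is an odds ratio or a log-odds-ratio, and make it agree with the stated relative reduction.
5. Keep the 5-point reduction as the consensus meaningful effect, but state the trial's power for it: about 40–56%, depending on the composite.
6. Describe the NNT as applying to the full primary outcome, including new MINS, in sections 1.2.4 and 9.1.

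The distribution has to come from the sponsor's own calculation; it should not be back-solved from 507 or taken from the illustrative splits used here. The cost is a protocol wording change and a less favourable description of the design. There is no change to the number of patients, the ranking or the primary test.

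### Section 9.1 equates a 30% relative risk reduction with a log-odds-ratio of 0.64; the two do not match at any rate the protocol assumes, and they imply different sample sizes

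*Protocol*

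**What the plan says.** The primary outcome is analysed as six ordered ranks with a Wilcoxon-Mann-Whitney test. The last paragraph of section 9.1 sets the effect: "To detect a 30% RRR (corresponding to a log-odds-ratio of approximately 0.64"). The model behind it is given as "assuming proportional odds (34) between the liberal and restrictive groups". The result reads: "we require a sample size of 507 participants in each arm, using a Wilcoxon-Mann-Whitney rank-sum test with a 5% two-sided significance level and 90% power". With 10% added for dropout, 507 becomes 563 per group and 1126 in total.

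The control-group inputs are death 7%, MACE 10% and new MINS 20% at 30 days. Section 9.1 adds that "we estimate a population 'usual care' MACE rate (including death) of 10% at 30 days" and that "components will occur concurrently in some participants". It gives neither the size of the overlap nor the proportions expected in the six ranks.

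A different effect appears earlier in section 9.1: "we consider an absolute risk reduction (ARR) of 5% in the primary outcome to be a realistic meaningful effect size that would change practice", described as a 33% RRR. The same 5% and 33% stand in the Scientific Abstract and in sections 1.2.4 and 3.1. Section 3.1 also gives an expected primary-outcome rate of 15%.

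**The concern.** A relative risk reduction converts to an odds ratio only at a stated control rate, and the sentence gives none for the composite. At the rates that the protocol does give, a 30% RRR falls well short of a log-odds-ratio of 0.64. One sentence therefore carries two effect sizes as if they were the same.

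This parameter fixes the size of the trial, in the protocol version that changed the primary outcome and cut the sample size from 1964 to 1126. An oversight committee or statistician who rebuilds the calculation from the printed log-odds-ratio with the usual ordinal method gets roughly half the planned number. One who uses the 30% RRR gets about the planned number, but only if the composite rate is near 30%.

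**Working it through.** **Inputs.** 5% two-sided significance, 90% power, 1:1 allocation: (1.960 + 1.282)² = 10.507. Rates are those of section 9.1. *Assumption:* because MACE is said to include death, non-fatal MACE is 10% − 7% = 3%. With no overlap, the control split is then 70% no event, 20% new MINS only, 3% non-fatal MACE and 7% death. Splitting death over ranks 4 to 6 (3/2/2) leaves the results below unchanged to within one participant. Other splits are shown because the overlap is not stated.

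**Step 1: the conversion.** For control rate p, a 30% RRR has OR = 0.7(1 − p)/(1 − 0.7p).

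| p | OR | absolute log OR |
|---|---|---|
| 15% | 0.665 | 0.41 |
| 20% | 0.651 | 0.43 |
| 30% | 0.620 | 0.48 |
| 37% | 0.595 | 0.52 |
| 52% | 0.527 | 0.64 |

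The component rates sum to at most 7 + 10 + 20 = 37%, so 52% is out of range. In the other direction, a log OR of 0.64 (OR 0.527) applied to a 30% rate gives an event rate of 18.4%, and 1 − 18.4/30 = 39% RRR.

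**Step 2: can 507 be reproduced?** Let p̄ be the rank proportions averaged over the two arms, and θ the probability that a control participant ranks worse than a liberal-arm participant, ties counted as half.

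- Proportional-odds formula (Whitehead): n per arm = 6 × 10.507 / [(log OR)² (1 − Σp̄³)]
- Rank-sum formula (Noether), no tie correction: n per arm = 10.507 / [6(θ − ½)²]
- The same with tie correction: multiply by (1 − Σp̄³)

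At 70/20/3/7:

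- *Log OR 0.64 as printed.* Σp̄³ = 0.440. Whitehead: 63.04/(0.4096 × 0.560) = 275. Noether with ties: 284. Noether without ties: θ = 0.5588, 10.507/(6 × 0.0588²) = 506.9 before rounding of θ. Simulated power of the tie-corrected test at 507 is 99%.
- *30% RRR on the any-event rate (log OR 0.478).* Whitehead: 63.04/(0.2281 × 0.581) = 476. Simulated power at 507 is 91%.
- *30% RRR in every component.* The common OR is 0.626 (log OR 0.469). Whitehead: 493. Noether with ties: θ = 0.545, 864.8 × 0.581 = 503. Simulated power at 507 is 90.4%.
- *0.64 read as an odds ratio (log OR 0.446).* Whitehead: 541.

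So 507 follows to within about 3% from a 30% RRR in each component. It also follows from a literal log OR of 0.64 in the formula that ignores ties.

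**Step 3: dependence on the unstated split (Whitehead, per arm).**

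| Control split | Any event | Log OR 0.64 | 30% RRR on any event |
|---|---|---|---|
| 63/20/10/7 | 37% | 235 | 348 |
| 70/20/3/7 | 30% | 275 | 476 |
| 80/10/3/7 | 20% | 382 | 802 |
| 85/5/3/7 | 15% | 492 | 1127 |

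For a 30% RRR, power at 507 is about 97%, 91%, 73% and 58% down the rows.

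**Step 4: the other effect sizes.** 5%/33% implies a 15% control rate, as section 3.1 states. But 15% cannot hold alongside 20% for new MINS alone. At a 30% composite, a 30% RRR is a 9-point absolute reduction, while a 5-point reduction is a 17% RRR.

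**The case against.** The strongest reply is that the number is sound and only a parenthesis is wrong. On the most direct reading of the stated rates, a 30% RRR in each component needs 493 to 503 per arm, and 507 gives about 90% power. That stands. A reader might infer from the faulty log-odds-ratio that 507 itself is an error or cannot be reproduced; the stated RRR and rates do not support that.

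A reader might also conclude that 0.64 is simply an odds ratio printed under the wrong name. It is plausible, since an OR of 0.64 is a 30% RRR at a control rate of about 24%. But the protocol does not assume 24%, and an OR of 0.64 gives 541 per arm at 70/20/3/7. The rival explanation, a true log-odds-ratio of 0.64 in a rank-sum formula without tie correction, returns 506.9. Section 9.1 names the rank-sum test and also cites an ordered-categorical sample-size reference for proportional odds, so the text does not settle which formula was used.

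Nor does the literal value always lead to a much smaller trial: at the 15% rate of section 3.1, a log-odds-ratio of 0.64 needs about 492 per arm. That does not rescue the sentence. At that rate 0.64 is a 43% RRR, and 15% conflicts with the 20% assumed for new MINS.

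**Conclusion.** The stated equivalence is false at every rate the protocol assumes: a 30% RRR is an absolute log-odds-ratio of 0.41 to 0.52 for composites of 15% to 37%, not 0.64. This part depends on no assumption about overlap or formula.

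The consequence for size does depend on the split. At 70/20/3/7 with a tie-adjusted method, the two effect sizes need about 275 and about 476 to 503 per arm, so 507 agrees with the RRR and disagrees with the printed log-odds-ratio. How 0.64 arose remains open. If it was the value used without tie correction, the problem goes beyond a label, because about three quarters of participants would share one rank. Even then 507 would give about 90% power for a 30% RRR at this split. If the composite is nearer 20%, power for a 30% RRR falls to about 73%.

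**What to change.** In section 9.1, replace the sentence with the odds ratio, the log-odds-ratio and the sample-size formula actually used, taken from the sponsor's own calculation. A value inferred from outside could misreport that calculation. Next to it, print the assumed control proportions for ranks 1 to 6, including the overlap between components, and restate the power at 507 per arm on that basis. Then reconcile the 30% RRR with the 15% composite rate, the 33% RRR and the 5% absolute reduction in the Scientific Abstract and sections 1.2.4, 3.1 and 9.1, so that one effect size and one composite rate appear throughout.

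The cost is a corrected sentence, a six-row table and consistent edits in those sections. Recruitment does not need to change if a 30% RRR on a composite of roughly 30% is confirmed. If another composite or effect size was intended, the power must be restated.
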